1.2. Research question

What are the effectiveness and safety of Tenofovir/ Emtricitabine in addition to the use of Personal Protective Equipment (PPE) for the prevention of SARS-CoV-2 infection in health care personnel who provide clinical care to confirmed or suspected cases of COVID-19 in the emergency room, COVID wards and ICU?

1.3. Theoretical framework

In December 2019 at Wuhan, the capital city of Hubei Province in China, there was a report of a conglomerate of pneumonia cases that alarmed health authorities of this country (16). Later, it was identified that the etiology of this acute respiratory infection is a novel coronavirus (SARS-CoV2) which shares some molecular characteristics with MERS-CoV (Middle East Respiratory Syndrome) and SARS-CoV1 (acute severe respiratory syndrome) (17)

The disease caused by SARS-CoV2 known as COVID-19 has a wide range of manifestations that vary from asymptomatic individuals to patients developing acute respiratory distress syndrome (ARDS). Also, it has been reported extrapulmonary manifestations such as gastrointestinal, dermatological, and CNS involvement (16,18). Some risk factors for mortality have been described, for instance, D-dimer greater than 1ug/ml, high SOFA score, and Advanced age (19).

Outbreaks from familial clusters in which the virus has been able to be identified have been described (20). To date there is no estimative of prevalence in asymptomatic patients due to the difficulty in identification techniques. Nevertheless, it has been documented that viral load is higher at the onset of symptoms indirectly pointing that transmissibility initiates 2.5 days before the initiation of symptoms which implies that people who develop symptoms could be infective even before that happens (18).

The epidemic has extended rapidly through the globe due to its high basic reproductive number, estimated on average between 2.5 to 3.6, this obtained from mathematical modeling (2,21,22). The burden of disease is serious making health systems exceed maximum capacity (22). According to the Pan-American Health Organization (PAHO) as of July 5th, there were 5.697.954 cases alone in the Americas with 262.538 deaths (23). In Colombia, the first case was reported on March 6 with a tendency to rise. Since then, multiple public health measures were taken gradually expecting to reduce transmissibility in the upcoming weeks. According to the Colombian National Institute of Health (INS), there has been an exponential increase in reported cases with data as of June 9 of 40.719 confirmed cases and 1.308 confirmed deaths (24).

The pandemic has presented a huge economic impact globally. The economic effect of this crisis is estimated to be serious and profound. Only the closure of Wuhan, a large financial center in mainland China, meant the suspension of activities of multinationals and the collapse of multiple stock markets around the world since before the internationalization of the epidemic (25). Although the extent of the current crisis is not yet known, it could be extrapolated from previous coronavirus outbreaks such as MERS in 2015, for which losses of approximately \$ 2.1 billion were estimated for tourism alone in the Republic of Korea (26). This outbreak was much smaller in terms of victims and geographic size. Meanwhile, the less conservative projections project declines in global GDP growth for the first quarter of zero and a substantial decline in growth in the world economy for the full year (25,277).

Natural history of SARS-CoV-2 / COVID 19

-Incubation period

Studies performed in confirmed cases of COVID-19 estimate an average incubation period of 5.5 days with a maximum expected of 12-14 days after the contact has occurred (28). Only between 1 to 5 % of reported cases will exceed that period of time thus making epidemiologic surveillance documents recommend a 14 day follow up after being in contact with an infected person (29-33).

-Previous period to onset of symptoms in which it is considered that persons can transmit the virus

The exact duration of the asymptomatic period in which the virus can be transmitted is unknown. It is estimated that this could be between 2 to 5 days prior to the onset of symptoms. Moreover, studies of follow up to close contacts state that an attack rate of 0.7 to 6.4% could be in this period (34,35). A mathematical model made in China establishes that infectivity is much higher in early stages of SARS-CoV-2 infection, initiating on average 2.3 days prior to the onset of symptoms with a peak at the day 0.7 after presence of symptoms and a considerable drop close to day 7 after initiation of symptoms (36).

-Calculated percentage of asymptomatic patients

There is still no clarity about the percentage of asymptomatic cases which increments the uncertainty and generates greater difficulties in order to establish infection control effective public health policies. Screening studies in confined population show frequencies of asymptomatic infected individuals between 18-46.5% (37). Nevertheless, surprisingly, up to 50% of these individuals could have radiological manifestations of COVID-19 (38,39).

-Average time of symptoms duration

The International Otorhinolaryngology Federation performed an observational study in which 1. 420 mild-moderate COVID-19 cases were assessed for describing clinical and epidemiological characteristics in Europe. The most frequent symptoms were Cephalalgia(70.3%), anosmia (70.2%) nasal congestion (67.8%), cough (63.2%), myalgias (62.5%), rhinorrhea (60.1%), dysgeusia (54.2%), odynophagia (52.9%) and fever (45.4%), respectively. Mean duration of symptoms was 11.5±5.7 days (40).

The China Medical Treatment Expert Group for COVID-19 retrospective cohort described 1,099 patients with SARS-CoV-2 confirmed infection finding that up to 88.7% of hospitalized patients developed fever followed by 67.8% of patients that developed cough. Mean duration of hospital stay was 12.8 which would correspond with the symptomatic period (41).

Impact and prevention measures in health care workers

The contagion in health care workers has been a critical point in the COVID-19 pandemic. Some series report that up to 19% of contagions occur in the health care setting (42). The main basic prevention measure is the use of personal protective equipment (PPE). Both WHO and the CDC recommend the use of standard precautions of contact and droplets with complete facial protection or at least ocular protection (42,43). Aerosol Isolation measurements are required only in the case of aerosol-generating procedures, such as orotracheal intubation or extubation, bronchoscopy, non-invasive mechanical ventilation, nebulization, Cardiopulmonary resuscitation, or endoscopy (21). For its part, the CDC recommends that patients with suspected or confirmed COVID-19 be cohorted in individual rooms with a door and an exclusive bathroom (42).

Special attention is given to the placement and removal sequence of PPE in order to avoid contagion when manipulating them. The effectiveness of the adequate use of PPE has not been established by a clinical trial, however, it is known that it is a protective factor for COVID-19 (44). Nevertheless, shortage of PPE, PPE re-use necessity and PPE use errors (especially when taking them out) might facilitate hand and mucous contamination, which may contribute to its ineffectiveness (45).

According to a report of the Colombian Social Protection Ministry, as of May 1st, 2020 6.5% of the total COVID-19 cases were from health care workers. A total of 459 cases from which 30.1% were nurse assistants, 23.7% were medical doctors, 15% were nurse practitioners and 2.4% were Respiratory therapists. Most of the cases were in Bogota (35.9%) followed by Risaralda (20%) and Cali (9.6%). Data on the burden and incidence of COVID-19 for health care workers is limited. Data from China reported an incidence of 38.9 per 100 exposed health care workers and 6 to 11.6 per 100 hundred health care workers in Madrid and The Netherlands respectively (7,44).

Tenofovir/Emtricitabine as prophylaxis for SARS-CoV-2 Infection

SARS-CoV-2 is a single strand positive-sense RNA virus similar to Hepatitis C Virus, West Nile Virus, Marburg, HIV, Ebola, Dengue virus, and Rhinovirus, among others. The RNA-dependent RNA polymerase (RdRp) is one of the structural proteins of SARS-CoV-2(46). The active site of RdRp is configured by two successive aspartate residues which protrude from a beta turn structure, making accessible to the surface through the nucleotide canal (47). The homology between SARS-CoV-2 RdRp and SARS-CoV-1 is higher than 97%, thus facilitating *in silico* studies (48).

Elfiky *et al.* made an RdRp SARS-CoV-2 model based on different available structures in protein banks. Using it and through simulation, they documented the theoretical effectiveness of several antiviral agents such as IDX-184, Sofosbuvir, Ribavirin y Remdisivir, and TDF/FTC for the inhibition of RdRp (47,49).

The antiretrovirals used in the treatment of HIV infection have been previously studied *in vitro* and *in vivo* for SARS (Severe Acute Respiratory Syndrome) and MERS (Middle East Respiratory Syndrome) (50,51). Particularly, in this pandemic some observational studies have identified a smaller number of patients with HIV acquiring COVID-19 in comparison to the general population which has brought attention to the scientific community (52).

In silico studies have identified antiretroviral drugs with potential capability of binding the catalytic center of RdRp such as Nucleoside Reverse Transcriptase Inhibitors: abacavir, emtricitabine, lamivudine, zidovudine and tenofovir, also protease inhibitors such as: lopinavir, ritonavir, saquinavir and the booster cobicistat (53-55). This information has been confirmed *in vitro* studies for TDF, which acts as analogue of a nucleotide that early finishes the replication of the RNA strand (55).

Cytotoxic and antiviral effects of some of the molecules have been evaluated in fibroblasts from human lung cells. For tenofovir and emtricitabine (TDF/FTC) the EC50 and the TC50 higher than 100 μ M, however, it is inferior compared to remdesivir which might be explain for the type of assembling to the RdRp in each case (48).

Furthermore, Park, *et al.* developed an animal model of SARS-CoV-2 in ferrets in which the pathogenicity, transmissibility, and lung damage caused by the virus were demonstrated. In an experiment using this model, the virus was inoculated by the intranasal route, and a day after, numerous molecules with potential antiviral effect were administrated. These molecules were: Lopinavir/Ritonavir, Hydroxychloroquine, TDF/FTC. The duration of the intervention was 14 days and the ferret group given TDF/FTC presented lower temperature compared to the control group, and also an earlier recovery from signs including cough, rhinorrhea, and reduction of activity. Moreover, a lower load of virus was detected in the nasal samples from ferrets in the intervention group. From the drugs studied TDF/FTC showed the best results in reducing clinical signs and clearing nasal viral shedding (46).

Tenofovir/Emtricitabine is an antiviral that has been widely used for quite a long time in HIV pre exposure prophylaxis (PrEP) and treatment for hepatitis B with a known security profile and minimal incidence of adverse events (10-13). Its inhibitory effect on the RdRp of SARS CoV 2 shown *in silico* studies is added to some animal models which makes it a promising alternative in a high risk COVID-19 population scenario. To date there are two ongoing clinical trials, one in Spain and the other in Argentina aiming to prove the effectiveness of TDF/FTC in the prevention of SARS CoV 2 infection. (See appendix 1).

Diagnostic testing

Various diagnostic tools based on the natural history of the diseases and experience obtained from other viruses have been proposed to have rapid results on the diagnosis status of the patient. Nevertheless, the power of viral identification varies according to the dynamics of the disease (57).

Available testing alternatives are viral RNA detection by real-time polymerase chain reaction (RT-PCR), viral antigen detection in nasopharyngeal swabs, specific antibodies detection, and viral culture. Antigen viral detection has low sensitivity in previous experience with HCOVs, however, there are studies ongoing with good yield according to with the reports of Diao *et al.* which

establish that the sensitivity is adequate in patients with 3-day fever, still at publishing stage (57). For its cost time and biosecurity required the viral culture has a research application but not a clinical one (57). Thus, basing the clinical diagnoses in the method RT-PCR and antibody detection.

During the COVID-19 outbreak, the RT-PCR has been one of the most used testing tools. Corman et al at Charité Hospital in Germany developed an RT-PCR identifying E and RdRP viral genes with a sensitivity greater than 95% and a specificity of 100% (58). It is important to clarify that detection varies from the site of the testing sample being positive in 32% of oropharyngeal swabs, 62% in nasopharyngeal swabs, and 80% from bronchoalveolar lavage. Only 15% of patients with pneumonia had positive serum RNA (59,60).

In symptomatic patient the viral load has its peak at the first week of symptoms (60% sensitivity before day 11), usually, around day 4 with a gradual decline starting on the second week, still being detectable in up to 33% of patients. The median of negativization is 24 days (IQR: 18-31 days) being lower in COVID-19 mild to moderate (13 days) and higher in critical patients (31 days) with detectable viral loads between 42 to 48 days after the onset of symptoms (36,61-64). Nevertheless, despite of the longtime of detectable viral load, there are studies suggesting that the viral culture negativize at day 8 from the onset of symptoms independently of initial viral load (65).

With regards to antibody detection, it is important to know that according to a Cochrane Systematic review, the yield of the different test available depends on the onset of symptoms and sample taking. IgG and IgM sensitivity at day 15 from the onset of symptoms is 75.4% and 88.2% respectively, whereas, at day 21 from the onset of symptoms is 99.1% and 98.7% (66). Although, a recent published study found a seroconversion rate of 10% in asymptomatic contacts evaluated after 14 days from the onset of symptoms, there is not certain data of sensitivity and specificity of this tests in asymptomatic people (67).

The detection of antibodies has been described even at the onset of symptoms; however, the general total antibody seroconversion starts at day 4 from the onset of symptoms. When evaluating IgM seroconversion, a 5-day median of positivization (IQR:3-6 days) with a sensitivity around 50% at day 7, higher than 70% after day 8 and highest after day 10 with a progressive decline over the next month (68). For IgG the positivization increases after day 9 with a median of 14 days (IQR:10.18 days) with a sensitivity between 80 to 95% at day 15 and 98 to 100% between the third and fourth week after the onset of symptoms with an IgG duration yet unspecified (68-73). Serologic testing may present crossed reactions with SARS-CoV explained by a 90.5% coincidence in the genomic sequence (74).

Data available on diagnostic testing is based on symptomatic patient. It has been described on several occasions since the beginning of the pandemic asymptomatic people with positive RT-PCR in respiratory secretions (69,70). However, the RT-PCR sensitivity and the ideal moment to perform it remains unclear with report as low as 24.3% (75).

Taking into consideration everything that has been discussed previously, we establish a research proposal in which it is planned to evaluate the efficacy and safety of Tenofovir/Emtricitabine and adequate use of PPE as a preventive measurement for COVID-19 in health care personnel.

2. Objectives

2.1. General Objective

To evaluate the effectiveness and safety of Tenofovir/ Emtricitabine in addition to the use of Personal Protective Equipment (PPE) for the prevention of SARS-CoV-2 infection in health care personnel who provide clinical care to confirmed or suspected cases of COVID-19 in the emergency room, COVID wards and ICU.

2.2. Specific Objectives

- To determine the effectiveness of Tenofovir Emtricitabine in addition to the use of Personal Protective Equipment (PPE) for the prevention of SARS-CoV-2 infection in health care personnel caring for patients with confirmed or suspected COVID-19 in the emergency room, general ward and ICU.
- To evaluate the safety (adverse events frequency) of Tenofovir Emtricitabine in addition to the use of Personal Protective Equipment (PPE) for the prevention of SARS-CoV-2 infection in health care personnel caring for patients with confirmed or suspected COVID-19 in the emergency room, general ward and ICU.
- To evaluate the adherence to Tenofovir Emtricitabine of health care personnel caring for patients with confirmed or suspected COVID-19 in the emergency room, general ward, and ICU.
- To determine the frequency of discontinuation for any reason of Tenofovir Emtricitabine in health care personnel caring for patients with confirmed or suspected COVID-19 in the emergency room, general ward, and ICU.
- To describe and compare the clinical course and severity of participants who develop COVID-19 in the intervention and control groups.

3. Methodology

3.1. Study design

Randomized triple-blinded multicentric clinical trial, conducted in parallel, with two arms:

The trial will be performed with health care workers (Physicians, Nurses, Respiratory therapists, or nurse assistants) free of SARS-CoV-2 infection prior, recent or at the time of the inclusion and who directly care for confirmed or suspected cases of COVID-19 in the emergency room, general COVID wards or intensive care units. A screening at baseline will be carried out in order to evaluate for eligibility by performing: SARS-CoV-2 RT-PCR, SARS-CoV-2 IgG antibodies, as well as, hemogram, creatinine, serum phosphorus, AST, ALT, ELISA for HIV, surface Hepatitis B antigen antibodies, qualitative pregnancy test (b-HCG). Once

eligibility is verified participants will be randomly assigned to either an intervention or a control group.

The interventions consists in the administration of Tenofovir/ Emtricitabine (300 mg / 200 mg daily during 60 days) + Personal Protective Equipment (PPE) and the control consists in the administration of placebo (1 tablet daily during 60 days) + Personal Protective Equipment (PPE)

All participants will have PPE recommended for the preventions of COVID-19 by the WHO which include mayo dress, nonfluid long sleeve gown, ocular protection with goggles, face shield or visor and surgical mask in procedures that do not aerosolize. N-95 respirators are required for procedure that generate aerosols. For detailed description see Table 2.

The re-use of N-95 respirators will be allowed according to CDC and WHO guidelines. This taking into consideration the shortage of supplies for the actual situation. The N-95 continuous use will be for 8 hours and the N-95 intermittent use will be allowed up to 5 times with the precaution of storage in a paper and plastic bag label them with the participant name and placed them in a plastic recipient at the end of shifts(48).

After baseline evaluation and confirming eligibility an initial visit and 4 follow up visits at day 20, 40, 60, 75 days will be carried out. See Table 1 and Graph 1.

In the case of presenting COVID-19 related symptoms at any time after enrolling a SARS-CoV2 RT-PCR will be performed between day 1 to 5 of the onset of symptoms and will be repeated it after 72 hours in case that the first one is negative. In the case of having any positive SARS-CoV2 RT-PCR or SARS-CoV2 IgG SARS-CoV2 infection will be confirmed and the intervention will be suspended.

On the other hand, the participant who develop symptoms and has one or two negative SARS-CoV2 RT-PCR the intervention will not be suspended with an exception if the participant requires hospitalization with a high clinical suspicion. For his group of participants, a SARS-CoV2 IgM and IgG antibodies will be performed at day 14 from the onset of symptoms. If they are positive, the participant Will be considered as a positive case of COVID-19.

3.2. Study population

-Reference population: Health care professionals (Physicians, Nurses, Respiratory therapists, or nurse assistants) between the ages of 18 and 70 years, who directly care for confirmed or suspected cases of COVID-19 in the emergency room, general COVID wards or intensive care units.

-Eligible population:

Inclusion criteria

- Medical doctor, Nurse, Respiratory therapist, or nurse assistant who work in the emergency room, general COVID-19 ward, or intensive care unit
- Age: between 18-70 years
- RT-PCR and serology tests for SARS-CoV-2 negative at baseline evaluation

- Direct care of patients in the emergency room, general COVID-19 ward, or intensive care unit
- Informed consent signed

Exclusion criteria

- Two or more of the following
 - ✓ Body temperature higher than 38 Celsius
 - ✓ Cough of recent onset (in the previous 10 days)
 - ✓ Dyspnea
 - ✓ Odynophagia
 - ✓ Malaise, fatigue
 - ✓ Acute diarrheal disease
- History of COVID-19 confirmed by RT-PCR or IgG antibodies
- Family member with suspected or confirmed COVID 19
- cohabitating with a suspected or confirmed case of COVID-19
- Hepatitis B anti-surface antigen antibodies lower than 10mU/ml at baseline evaluation
- Acute or chronic Hepatitis B
- Confirmed diagnosis of HIV infection either by clinical history or ELISA immunoassay at baseline evaluation
- Use of TDF/FTC in the last three months for other clinical conditions
- ALT or AST higher than 2 times the upper reference limit
- Serum hemoglobin <11g/dl or neutropenia<1.000cell/mm³
- Renal dysfunction defined as eGFR lower than 60ml/min (using the CKDEPI formula) or history of Chronic kidney disease
- Known hypersensitivity to TDF/FTC
- Serum phosphorus level <2.5mg/dl
- Use of the following medications (for detailed description see appendix 2):
- Uso de los siguientes medicamentos (See appendix 2 for detailed description): Cidofovir, Celecoxib, Diclofenac, Ibuprofen, Methadone, Naproxen, Nimesulide, Piroxicam, Amiodarone, Quinine, Amikacin, Cephalexin, Clarithromycin, Gentamicin, Piperacillin / Tazobazorcin, Flucomycin, Sulfadiazine, Vancomycin , Ganciclovir, Ledipasvir / Sofosbuvir, Sofosbuvir / Velpatasvir, Furosemide, Hydralazine, Sacubitril, Verapamil, Interferon, Hydroxyurea, Dolutegravir / Lamivudine Abacavir, Didanosine, Lamivudine, Atazanavir / cobicistat, Atazanavir / ritonavir, Darunavir / ritonavir, Darunavir / cobicistat, Indinavir, Interferon, Hydroxyurea, Cyclosporine, Mycophenolate, Sirolimus, Tacrolimus, Acetazolamide Orlistat, Probenecid, Pyridostigmine, Sevelamer, Zoledronic acid.
- Diagnosed osteopenia or osteoporosis
- History of pathological fractures
- Pregnancy, lactation, or pregnancy desire during the period of the study
- Being a participant in another Clinical trial of prevention for COVID-19

-Source population: Health care professionals (Physicians, Nurses, Respiratory therapists, or nurse assistants) between the ages of 18 and 70 years, who directly care for confirmed or suspected cases of COVID-19 in the emergency room, general COVID wards or intensive care units from seven health care institutions in Colombia (Hospital Universitario San Ignacio, Clínica Reina Sofía, Clínica Universitaria Colombia, Clínica Santa María de Lago, Hospital Universitario Nacional, Hospital Universitario de la Samaritana. Sede Bogotá y Hospital Universitario de la Samaritana. Sede Zipaquirá, Hospital Universitario San Jorge de Pereira).

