3.6. Procedures

In table 1. Detailed follow up evaluations are described.

Table 1. Description of the evaluations to be done during the trial.

Follow up table				
Day	General activity	Specific activity	Responsible	Result
0	Base line diagnoses	Initial Clinical evaluation	Medical doctor of the study	Evaluating inclusion and exclusion criteria. Signing informed consent form
		Blood samples	Nurse Lab tech	Laboratory report: hemogram, creatinine, phosphorus, AST, ALT HIV ELISA, HB Surface antigen antibodies
		SARS-CoV-2 RT-PCR sampling	Respiratory therapist or nurse	Result of SARS-CoV-2 RT-PCR
		SARS-CoV-2 IgM and IgG antibodies	Nurse Lab tech	Result of IgM and IgG antibodies
		b-HCG sampling in women	Nurse Lab tech	Report of b-HCG
20	Visit 1	Clinical evaluation	Medical doctor of the study	Clinical record and eCRF for clinical evaluation, adherence, and adverse events

40	Visit 2	Blood sample for: SARS-CoV2 IgM, IgG antibodies and blood chemistry	Nurse Lab tech	Laboratory report of SARS-CoV2 IgM, IgG antibodies and creatinine
		Clinical evaluation	Medical doctor of the study	Clinical record and eCRF for clinical evaluation, adherence, and adverse events
60	Visit 3	Blood samples	Nurse Lab tech	hemogram, creatinine, phosphorus, AST, ALT HIV ELISA, HB Surface antigen antibodies b- HCG in women
		SARS-CoV-2 RT-PCR sampling	Respiratory therapist	Result of SARS-CoV-2 RT-PCR
		Clinical evaluation	Medical doctor of the study	Clinical record and eCRF for clinical evaluation, adherence, and adverse events
75	Visit 4	Blood samples	Nurse Lab tech	Laboratory report of SARS-CoV2 IgG
		Clinical evaluation	Medical doctor of the study	Clinical record and eCRF for clinical evaluation,
		End of follow up and communication to study subject	Clinical coordinator	Minutes

During follow up to any participant who develop COVID-19 related symptoms at any time after randomization given by two or more of the following: Body temperature higher than 38 Celsius, cough of recent onset (in the previous 10 days), dyspnea,odynophagia, malaise, fatigue, acute diarrheal disease, ageusia, dysgeusia, anosmia or hyposmia, an RT-PCR will be performed within the next 5 days and will be repeat it if the result is negative and the symptoms persist. This RT-PCR will be performed at every of the centers of the study and will request the patient the immediate report of the symptoms through an app or via phone call. In case of a positive RT-PCR the infection

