3.6.2. Baseline evaluation

The doctor assigned to the study takes a medical history that includes a review of systems, past medical history, and a complete physical examination. In addition, he or she will order laboratory exams described in Table 1. In case of clinical or laboratory alteration defined in the exclusion criteria, the volunteer will be excluded and will not continue in the following phases. Additionally, a RT-PCR will be carried out with a nasopharyngeal swab sample and a serological test of IgG antibody titers against SARS-CoV-2. In case of having any of the previously mentioned tests positive, the volunteer will be excluded. Female volunteers will undergo qualitative β -HCG and, if positive, they will be excluded or if they report the desire to become pregnant in the next two months. At 24 to 48 hours with the results of the examinations and a new anamnesis the eligibility of the volunteer will be confirmed. If so, the randomization process will be carried out and the intervention will be delivered according to the process defined in the concealment section of allocation (3.6.4) and administration of the intervention product or placebo (3.6.5).

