Appendix 3. Variables

Inclusion-exclusion criteria

Variable	Variable type	Conceptual definition	Operative definition
Informed consent signature date	Quantitative	Informed consent signature date	Day/Month/Year
Age	Qualitative/dichotomous	Age 18 to 70 years according to legal ID	0- No 1- Yes
Profession	Qualitative/nominal	Profession	1- Physician 2- Nurse 3- Nursing assistant 4- Respiratory therapist
Caring for COVID-19 patients	Qualitative/dichotomous	Subject has direct contact with confirmed or suspected COVID-19 patients	0- No 1- Yes
Serology IgG for SARS-CoV-2	Qualitative/dichotomous	Result of serology IgG test for COVID-19 before randomization and administration of drug/placebo	0- Negative 1- Positive
Baseline RT-PCR for SARS-CoV-2	Qualitative/dichotomous	Result of RT-PCR for SARS-CoV-2 of nasopharyngeal swab before randomization and administration of drug/placebo	0- Negative 1- Positive
Exclusion criteria			
COVID-19 related symptoms	Qualitative/dichotomous	Presence of two or more of the following at initial screening: - Body temperature ≥ 38 °C - Acute cough (onset less than 10 days) - Shortness of breath - Sore throat - Malaise. - Acute diarrhea	0- No 1- Yes

History of COVID-19	Qualitative/dichotomous	History of serology or rtPCR confirmed COVID-19	0- No 1- Yes
Cohabitation with people with COVID-19 infection or COVID-19 symptoms	Qualitative/dichotomous	Cohabitation with people with COVID-19 infection or COVID-19 symptoms	0- No 1- Yes
Treatment during last month with medications that have significant interactions with TDF/FTC	Qualitative/dichotomous	Treatment during last month with medications that have significant interactions with TDF/FTC (see Appendix 2)	0- No 1- Yes
HIV infection	Qualitative/dichotomous	Confirmed HIV infection	0- No 1- Yes
B hepatitis immunity	Qualitative/dichotomous	Volunteer with anti-HBsAg less than 10 UI/ml	0- No 1- Yes
Hepatitis B infection	Qualitative/dichotomous	History of hepatitis B virus infection	0- No 1- Yes
Recent use of TDF/FTC	Qualitative/dichotomous	Use of TDF/FTC within the last month for any other indication	0- No 1- Yes
Hypophosphatemia	Qualitative/dichotomous	Phosphorus serum concentration less than lower reference laboratory value	0- No 1- Yes
Liver dysfunction	Qualitative/dichotomous	Liver dysfunction as defined by ALT or AST levels \geq 2 times upper limit of normal (x ULN) (66)	0- No 1- Yes

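### The baseline symptom exclusion is narrower than the follow-up testing trigger: it leaves out loss of smell and taste, so a few infections missed by the baseline tests could enter and count as primary events (minor)

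*Combined protocol and SAP*

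**What the plan says.** Baseline. Section 3.2 excludes volunteers with "Two or more of the following": fever, recent cough, dyspnea, odynophagia, malaise or fatigue, and acute diarrhea. The COVID-19 related symptoms row under the exclusion criteria in Appendix 3 repeats the rule ("Presence of two or more of the following at initial screening") with the same six items.

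Follow-up. Section 3.6 (Procedures) applies the same two-symptom threshold after randomisation, but its list continues with "acute diarrheal disease, ageusia, dysgeusia, anosmia or hyposmia, an RT-PCR will be performed within the next 5 days".

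Laboratory screen. Section 3.2 also requires "RT-PCR and serology tests for SARS-CoV-2 negative at baseline evaluation". Section 3.6.2 states the consequence of a positive result: "In case of having any of the previously mentioned tests positive, the volunteer will be excluded". A further history is taken 24 to 48 hours later, before randomisation.

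Outcome. Section 3.3 counts any positive RT-PCR or IgG during follow-up as a primary event. The statistical analysis plan (section 4) starts the clock at randomisation. Neither sets aside positives found soon after entry.

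**The concern.** The two lists serve related purposes and share a threshold, yet they differ in the four smell and taste items, and the protocol gives no reason. The case series in section 1.3 reports anosmia in 70.2% and dysgeusia in 54.2% of mild to moderate cases, both above fever at 45.4%. The baseline list keeps fever and drops the two more frequent symptoms.

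At stake is the section 3.1 condition that participants be free of infection at inclusion. Prophylaxis cannot prevent an infection that is already present. Such infections fall about equally in both arms, count as incident events, and pull the estimated effect toward no difference.

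**Working it through.** **1. The lists side by side**

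| Symptom | Baseline exclusion (3.2, Appendix 3) | Follow-up trigger (3.6) |
|---|---|---|
| Fever, cough, dyspnea, odynophagia, malaise/fatigue, diarrhea | yes | yes |
| Ageusia, dysgeusia, anosmia, hyposmia | no | yes |
| Threshold | two or more | two or more |

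Anosmia plus cough, or anosmia plus dysgeusia, meets the second rule and not the first.

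**2. Do the baseline tests close the gap?** Not fully. Section 1.3 gives "60% sensitivity before day 11" for RT-PCR in symptomatic patients, 62% positivity for nasopharyngeal swabs (the specimen used at baseline), and a median of 14 days to IgG positivity. In follow-up, one negative RT-PCR in a symptomatic participant leads to a repeat and to antibodies at day 14 (section 3.1). No such step is specified at baseline. The 24 to 48 hour history confirms eligibility against the same criteria, so it carries the same omission.

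**3. The plan's own figure (section 3.4).** Risks 0.10 and 0.05, power 0.80, alpha 0.05 (two-sided assumed):

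n per arm = [1.96 × √(2 × 0.075 × 0.925) + 0.8416 × √(0.09 + 0.0475)]² / 0.05² = 435.

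The plan states 429, which is within 1.4%. Power at 429 per arm is 79.5%.

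**4. Share of symptomatic cases between the lists.** Symptoms are assumed independent. With P0 and P1 the probabilities of none and exactly one baseline symptom, and anosmia and dysgeusia as the added items:

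share = P0 × (0.702 × 0.542) + P1 × (1 − 0.298 × 0.458) = 0.3805 × P0 + 0.8635 × P1.

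- Only the three baseline symptoms with a frequency in section 1.3 (cough 63.2%, odynophagia 52.9%, fever 45.4%): P0 = 0.0946, P1 = 0.3475, share = 0.336.
- Adding malaise at 62.5% (the myalgia figure as proxy) and, as pure assumptions, dyspnea 30% and diarrhea 30%: P0 = 0.0174, P1 = 0.1077, share = 0.100.

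**5. From share to participants.** Assume 10% incidence over 60 days (the control risk in section 3.4, spread evenly), a 14-day window before IgG, all infections symptomatic, and 40% false-negative RT-PCR:

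- Infected and not yet IgG positive on the screening day: 0.10 × 14/60 = 2.33%.
- Fraction entering through the gap: k = 0.0233 × share × 0.40 = 0.09% (share 0.100) to 0.31% (share 0.336).
- Of 950: 0.9 to 3.0 people.

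**6. Effect on the planned contrast.** Each arm's risk becomes k + (1 − k) × p.

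| k | Control | Active | Risk ratio | Power, 429 per arm |
|---|---|---|---|---|
| 0 | 0.1000 | 0.0500 | 0.500 | 79.5% |
| 0.09% | 0.1008 | 0.0509 | 0.505 | 79% |
| 0.31% | 0.1028 | 0.0530 | 0.515 | 78% |

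**7. Range.** At the site incidences in section 3.4, 3.3% gives about 0.3 to 1.0 people. At 13.7% the figure is 1.2 to 4.1 people, with a risk ratio of at most 0.521. Section 1.3 also cites above 95% sensitivity for one RT-PCR assay; at 95% and 10% incidence the count is 0.1 to 0.4.

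**The case against.** The symptom list is not the main barrier. Every volunteer must be negative on RT-PCR and serology, has a second history before randomisation, and is excluded if a family member or cohabitant is a suspected or confirmed case. Section 3.4 indicates that the institutions screen at least their symptomatic staff. The route needs a symptomatic volunteer with fewer than two listed symptoms, a false-negative RT-PCR and no IgG yet. This stands, and it is why the count is small.

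A reader might infer that someone with anosmia and cough at screening is already a case under the trial's own definition. The documents do not support that. The section 3.6 list prompts a test, and it speaks of symptoms that arise after randomisation. Infection is defined by RT-PCR or IgG in section 3.3, and section 3.1 counts a symptomatic participant with negative RT-PCRs as a case only if later antibodies are positive.

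It is also fair that aligning the lists leaves presymptomatic, asymptomatic and single-symptom infections untouched. None of this explains why a screen that the protocol chose to add to the tests should be narrower than its own trigger.

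**Conclusion.** The mismatch is certain and unexplained. The consequence is a narrow route by which a missed prevalent infection can enter and count as a primary event. The expected bias is toward no difference and does not create a false benefit. Its size is not in the documents. On the assumptions in the working it is about 1 to 3 of 950 participants, a risk ratio of about 0.505 to 0.515 instead of 0.50, and a loss of about one percentage point of power.

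The 10% to 34% share is an illustration and not a bound. The upper figure treats three listed baseline symptoms as absent, the lower uses frequencies that the documents do not give, and both assume independence. Treating all infections as symptomatic is generous, since section 1.3 puts 18% to 46.5% as asymptomatic. The risk ratio stands in here for the planned hazard ratio.

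A reader might infer a larger dilution, to a risk ratio of 0.52 to 0.58, by supposing that 0.5% to 2% of those randomised are already infected. That would cover infections from every route. For this gap alone to produce even 0.5%, between 0.005/(0.40 × 0.336) = 3.7% and 0.005/(0.40 × 0.100) = 12.5% of those screened would have to be infected, symptomatic and not yet IgG positive on the screening day. Section 3.4 reports 3.3% to 13.7% over two whole months. This is a minor point.

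**What to change.** Reconcile the two lists. Use the section 3.6 symptom list for the two-symptom baseline exclusion in section 3.2 and in the matching Appendix 3 row, and apply that list again at the 24 to 48 hour history already required by section 3.6.2. The change is one line of protocol text and one CRF row. The downside is a few more screen failures. The sample size of 858, raised to 950, does not change.

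Optionally, a pre-specified sensitivity analysis that sets aside events soon after randomisation, by the same rule in both arms, would also cover infections that no symptom list can catch.
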